#### 5.7.4 Clinical Endpoints

The following clinical endpoints will be reported for the Device and Control groups. For endpoints where a baseline measurement and post-treatment measurements are collected, the change from baseline will be summarized by time-point for each group and compared between Control and Device groups.

- Kaplan-Meier freedom from the components of the primary safety composite at 12 months, 24 months and yearly through 5 years (Device group only). Deaths and withdrawals will be censored in the analysis
- Kaplan-Meier freedom from the primary safety composite at 24 months and yearly through 5 years (Device group only)
- Kaplan-Meier freedom from all-cause mortality at 12 months, 24 months and then yearly through 5 years
- Kaplan-Meier freedom at 12 months, 24 months and then yearly through 5 years from:
  - 1) cardiovascular mortality
  - 2) the first HF related hospitalization

- 3) the first cardiovascular hospitalization
- 4) the first HF related hospitalization or all-cause mortality
- Proportion of MR Severity Grade < 2+ at 30 days, 6 months, 12 months, 24 months, and then yearly through 5 years.
- NYHA Functional Class at baseline, 30 days, 6 months, 12 months, 24 months and then yearly through 5 years
- Proportion of >1 class improvement of NYHA Functional Class at 30 days, 6 months, 12 months, 24 months, and then yearly through 5 years from baseline.
- Mean change in NYHA Functional Class at 30 days, 6 months, 12 months, 24 months and then yearly through 5 years from baseline.
- 6MWD at baseline, 30 days,6 months,12 months and 24 months (and change from baseline to follow-up)
- KCCQ QoL scores at baseline, 30 days,6 months, 12 months and 24 months (and change from baseline to follow-up)
- SF-36 QoL scores at baseline, 30 days, 6 months, 12 months and 24 months (and change from baseline to follow-up)
- Mitral valve surgery (including type of surgery), new use of CRT, new use of single
  or dual chamber pacemaker, permanent LVAD implant, heart transplant, additional
  MitraClip device intervention in Device group or *de novo* MitraClip device
  intervention in Control group, including reason for intervention through 5 years
- Responder analysis for 6MWD, where responder is defined as alive and experiencing an improvement of 24 meters and 50 meters (difference in proportion of responders between Device and Control groups) at 12 months and 24 months
- Responder analysis for LVEDV Index, where responder is defined as alive and experiencing an improvement of 12 ml/m^2 (difference in proportion of responders between Device and Control groups) at 12 months, 24 months and then yearly through 5 years
- Responder analysis for QoL (KCCQ), where responder is defined as alive and experiencing an improvement of 5 points (difference in proportion of responders between Device and Control groups) at 12 months and 24 months
- Each subscale for QoL (KCCQ) (difference in means between Device and Control groups) at 12 months and 24 months
- Length of index hospitalization for MitraClip procedure (Device group)

- Number of hospitalizations and reason for hospitalizations (i.e., HF, cardiovascular, non-cardiovascular) at 12 months and 24 months in each of the Device and Control groups
- Number of days alive and out of hospital from the time of randomization (difference in medians between Device and Control groups) to 12 months, 24 months and then yearly through 5 years
- Number of days hospitalized from the "Treatment" visit (difference in medians between Device and Control groups) at 12 months, 24 months and then yearly through 5 years
- Proportion of alive time in hospital will be summarized and compared between Device and Control groups at 12 months, 24 months and then yearly through 5 years
- Proportion of subjects living in the baseline location at 12 months, 24 months and then yearly through 5 years
- Mitral valve replacement rates will be summarized and compared between Device and Control groups at 12 months, 24 months and then yearly through 5 years
- New onset of permanent atrial fibrillation at 12 months, 24 months and then yearly through 5 years
- Mitral stenosis at 12 months, 24 months and then yearly through 5 years
- Clinically significant atrial septal defect (ASD) that requires intervention at 12 months,24 months and then yearly through 5 years
- Device-related complications in Device group subjects and Control group subjects who undergo MitraClip procedure through 5 years
- BNP (Brain Natriuretic Peptide) or NT-pro BNP (N-terminal prohormone of Brain Natriuretic Peptide) levels at baseline, 30 days, and 12 months
- Modified Rankin Scale Score at baseline, 30 days, 6 months, 12 months
- Major bleeding at 30 days
- Prolonged ventilation at 30 days
- Compliance with Guideline Directed Medical Therapy (GDMT) at baseline, 30 days, 6 months, 12 months, 24 months, and then yearly through 5 years
- Average dosages of Guideline Directed Medical Therapy (GDMT) at baseline, 30 days, 6 months, 12 months, 24 months, and then yearly through 5 years

- The number of (1) any changes in GDMT and GDMT dosage from baseline at 30 days, 6 months, 12 months, 24 months, and then yearly through 5 years and (2) any changes in GDMT from baseline that result in a larger than 100% increase or 50% decrease in dose at 30 days, 6 months, 12 months, 24 months, and then yearly through 5 years
- The reasons for any changes in GDMT from baseline at 30 days, 6 months, 12 months, 24 months, and then yearly through 5 years

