7.6.4 Clinical Endpoints

The following clinical endpoints will be reported for the Device and Control groups:

- Kaplan-Meier freedom from the components of the primary safety composite at 12 months, and yearly through 5 years (Device group only)
- Kaplan-Meier freedom from the primary safety composite at 24 months and yearly through 5 years (Device group only)
- Kaplan-Meier freedom from all-cause mortality at 12 months, 24 months and yearly through 5 years
- Kaplan-Meier freedom from: (1) cardiovascular mortality (2) the first HF related hospitalization (3) the first cardiovascular hospitalization (4) the first HF related hospitalization or all-cause mortality at 12 months and 24 months and then yearly through 5 years

- NYHA Functional Class at baseline, 30 days, 6 months, 12 months, 24 months and then yearly through 5 years
- 6MWD at baseline, 30 days, 6 months, 12 months and 24 months (and change from baseline to follow-up)
- KCCQ QoL scores at baseline, 30 days, 6 months, 12 months and 24 months (and change from baseline to follow-up)
- SF-36 QoL scores at baseline, 30 days, 6 months, 12 months and 24 months (and change from baseline to follow-up)
- Mitral valve surgery (including type of surgery), new use of CRT, new use of single or dual chamber pacemaker, permanent LVAD implant, heart transplant, additional MitraClip device intervention in Device group or *de novo* MitraClip device intervention in Control group, including reason for intervention through 5 years
- Responder analysis for 6MWD, where responder is defined as alive and experiencing an improvement of 24 meters and 50 meters at 12 months (difference in proportion of responders between Device and Control groups) at 12 months and 24 months
- Responder analysis for LVEDV Index, where responder is defined as alive and experiencing an improvement of 12 ml/m² (difference in proportion of responders between Device and Control groups) at 12 months, 24 months and then yearly through 5 years
- Responder analysis for QoL (KCCQ), where responder is defined as alive and experiencing an improvement of 5 points (difference in proportion of responders between Device and Control groups) at 12 months and 24 months
- Each subscale for QoL (KCCQ) (difference in means between Device and Control groups) at 12 months and 24 months
- Length of index hospitalization for MitraClip procedure (Device group)

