#### 5.7 Analysis of Additional Descriptive Endpoints

All additional endpoints in this section will be reported with descriptive statistics. Continuous endpoints will be summarized using the following: mean, standard deviation, median, the first and third quartiles, range, and the 95% confidence interval for the population mean using the normal approximation. Categorical endpoints will be summarized as proportions in the form of fractions and percent. The 95% confidence interval for a population proportion will be constructed using the Clopper-Pearson exact method. The 95% confidence interval for the difference of two proportions will be constructed using the Newcombe score method. Other analyses are specified under each category of additional descriptive endpoints.

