#### 5.8.2 Primary Effectiveness Endpoint

That Require Non-elective Cardiovascular Surgery Total

At least ten thousand (10,000) simulations with converged joint frailty model were performed to calculate sample size and power for the primary effectiveness endpoint. With a fixed sample size design, 610 subjects provide approximate 80% power at the one-sided significance level of 5% for the primary effectiveness endpoint.

The following assumptions were made for the calculation of sample size:

- The enrollment rate is based on the actual monthly enrollment numbers from December 2012 to February 2016, then 20 subjects per month, thereafter
- Attrition due to withdrawals at 12 months is 7.5% in both groups
- In the EVEREST High Risk Cohort (N = 211), the lower bound of a 95% confidence interval on the HF hospitalization rate in the period pre-enrollment was ~0.6 per 12 months. The HF hospitalization rate in the Control group is therefore assumed to be 0.6 per 12 months. The HF hospitalization rate in the Device group is assumed to be 0.42 per 12 months (30% Relative Risk Reduction).
- Subjects are followed for a minimum of 12 months. All available follow-up through 24 months at the time of data cut-off will be included in the analysis.
- The mortality rate in the Control group is 27%, and in the Device group is 22%.
- To account for informative censoring of death event, a shared random effect (frailty) model for recurrent events and terminal event is used to simulate recurrent events and

death event data. The correlation between these two processes is introduced by the shared frailty distribution, Gamma distribution with mean of 1 and variance of 1. The frailty is assumed to have the same impact on the hazards for recurrent and terminal event (e.g. frailty exponent is 1). The frailty variance and frailty exponent values are estimated and determined based on the REALISM HR FMR patients data and blinded pooled COAPT roll-in and randomized data as of June, 2016. The key underlying assumptions of the JFM are

- a) The recurrent, terminating, and censoring processes all have continuous distribution so that recurrent events and death cannot happen at the exact same time.
- b) Death event precludes the observation of new recurrent HF hospitalization events, but independent censoring (e.g. withdrawal or lost-to-follow-up) does not interrupt the occurrence of recurrent HF hospitalization events.

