#### A.2 CMS Subgroup Analysis

The following clinical outcomes will be analyzed by age subgroups (Age < 65 vs. Age  $\ge 65$ ) using Kaplan-Meier estimates. The treatment comparison in the age subgroup analysis is not powered for hypothesis testing and is not meant for confirmatory inference. Comparisons will be made between treatment arms within each age subgroup.

- Stroke at 12 months
- Major vascular complications (events) at 12 months
- Renal complications at 12 months
- All-cause mortality at 12 months

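### Kaplan-Meier curves for first HF hospitalization, first CV hospitalization and CV death overstate event probabilities because competing deaths are in effect censored; cumulative incidence should be added

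*SAP*

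**What the plan says.** SAP 5.7.4 reports, for Device and Control, "Kaplan-Meier freedom at 12 months, 24 months and then yearly through 5 years from" four outcomes: CV mortality, first HF-related hospitalization, first CV hospitalization, and first HF hospitalization or death from any cause. Protocol 4.5.4 and 7.6.4 carry the same list, in part "2) the first HF related hospitalization (3) the first cardiovascular hospitalization".

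That item does not say how deaths are handled. The nearest rule in SAP 5.7.4 belongs to a different item, the components of the primary safety composite through 5 years: "Deaths and withdrawals will be censored in the analysis".

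SAP A.2 analyses stroke, major vascular complications, renal complications and all-cause death by age subgroup "using Kaplan-Meier estimates". SAP A.1 summarizes the same non-fatal outcomes as simple proportions.

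For the primary endpoint, SAP 5.8.2 takes a different view of death: "To account for informative censoring of death event, a shared random effect (frailty) model for recurrent events and terminal event is used" to generate the planning data.

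On status, SAP 5.7 says "All additional endpoints in this section will be reported with descriptive statistics". Protocol 4.5 ties labeling claims to the primary and secondary endpoints.

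**The concern.** Death prevents a later hospitalization, and non-CV death prevents a later CV death. A Kaplan-Meier estimate for one such event has no standard way to handle the competing death except to censor it. It then treats the dead as if they stayed at risk with the same future hazard as the survivors. One minus that curve is not the proportion of patients who have the event; it is larger.

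This matters here because planned mortality is high (27% and 22% at 12 months), the horizon is 5 years, and the primary analysis rests on death being informative for HF hospitalization. These curves make the opposite assumption about the same deaths. At stake are the reported absolute event rates in each arm and the absolute difference between arms. Item 4, first HF hospitalization or death, is unaffected because death is part of the event.

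**Working it through.** **Inputs.** SAP 5.8.2: "The HF hospitalization rate in the Control group is therefore assumed to be 0.6 per 12 months"; Device 0.42 per 12 months; mortality 27% Control and 22% Device, taken as 12-month figures as SAP 5.8.3.2 states; shared gamma frailty with mean 1 and variance 1, acting equally on both processes. SAP 5.8.4.1: about 70% of deaths are CV. The hospitalization rate is taken as the hazard at frailty 1, and hazards are held constant over time given frailty.

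**Check of the inputs against the plan's own figure.** The documents give no Kaplan-Meier or cumulative incidence value for these endpoints. The stated figure built on the same inputs is the primary power of about 80% with 610 subjects at one-sided 5%. A simulation with these rates, 7.5% yearly attrition and a joint frailty fit gave 76.5% to 81.2% over a range of assumed accrual patterns (Monte Carlo standard error about 1 point). The inputs therefore reproduce the plan.

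**Formulas.** Let l be the event hazard, m the competing hazard and t years.
- Constant independent hazards: 1-KM = 1 - exp(-lt); CIF = l/(l+m) × (1 - exp(-(l+m)t)), where CIF is cumulative incidence.
- Gamma frailty, variance 1: 1-KM = 1 - (1+(l+m)t)^(-l/(l+m)); CIF = l/(l+m) × (1 - 1/(1+(l+m)t)).

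**Death hazard.** Constant: Control -ln(0.73) = 0.3147, Device -ln(0.78) = 0.2485. Frailty: Control 0.27/0.73 = 0.3699, Device 0.22/0.78 = 0.2821.

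**Control, 24 months, first HF hospitalization.**
- Frailty: l+m = 0.9699, l/(l+m) = 0.6187, 1+(l+m)t = 2.9397. So 1-KM = 1 - 2.9397^(-0.6187) = 48.7% and CIF = 0.6187 × (1 - 1/2.9397) = 40.8%.
- Constant: 1-KM = 1 - exp(-1.2) = 69.9%; CIF = 0.6/0.9147 × (1 - exp(-1.8294)) = 55.1%.

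All first HF hospitalization results, as 1-KM vs CIF:

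| Time, model | Control | Device | Arm difference (points) |
|---|---|---|---|
| 24 months, frailty | 48.7% vs 40.8% | 40.8% vs 34.9% | 7.8 vs 5.9 |
| 24 months, constant | 69.9% vs 55.1% | 56.8% vs 46.3% | 13.1 vs 8.7 |
| 5 years, frailty | 66.5% vs 51.3% | 59.4% vs 46.6% | 7.1 vs 4.7 |
| 5 years, constant | 95.0% vs 64.9% | 87.8% vs 60.6% | 7.3 vs 4.3 |

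The overstatement under frailty is thus 5.9-7.9 points at 24 months and 12.8-15.2 at 5 years; with constant hazards it is 10.5-14.8 and 27.1-30.1. Simulating 400,000 subjects per arm under frailty, with attrition, gave the same values to within about 0.2 points.

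**CV death.** Here l is 70% and m is 30% of the death hazard. At 24 months the excess is 2.4-2.9 points in Control and 1.6-2.0 in Device. At 5 years it is 6.5 (52.0% vs 45.4%) to 11.3 (66.8% vs 55.5%) in Control and 5.0 (46.0% vs 41.0%) to 8.3 (58.1% vs 49.8%) in Device. Varying the CV share from 50% to 90% gives 2.0-14.8 points at 5 years.

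**First CV hospitalization.** No rate is given. If it is assumed to lie between the HF rate and the all-cause rate in SAP 5.8.4.8 (1.9 Control, 1.4 Device), the excess is about 6-16 points at 24 months and 10-30 at 5 years.

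**The case against.** The strongest reply has four parts.

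**The endpoints are descriptive.** They are outside the testing sequence in SAP 5.9 and no labeling claim rests on them. This stands, and it limits the consequence to reporting.

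**Competing death is already addressed elsewhere.** The multi-state model in SAP 5.6.1.9 has death as a state with separate transitions. The Finkelstein-Schoenfeld analysis, the win ratio, days alive and out of hospital, and the composite with death all account for it. A reader might infer that the plan ignores competing death altogether; it does not. SAP A.1 also uses proportions that exclude only lost or withdrawn subjects, so by its wording deaths stay in the denominator. But the multi-state model is planned to give hazard ratios, and none of these analyses gives the probability of a first HF hospitalization, first CV hospitalization or CV death over time.

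**The distortion of the arm difference is modest.** Under frailty it is 7.8 - 5.9 = 1.9 points. With 305 per arm and before censoring, the standard error of the difference is about sqrt((0.487×0.513 + 0.408×0.592)/305) = 4.0 points. That stands for the difference. For a single arm it does not: in Control the excess is 7.9 points against sqrt(0.487×0.513/305) = 2.9.

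**The choice is one of estimand.** Cumulative incidence mixes the mortality effect into the hospitalization comparison, since the arm with fewer deaths keeps more patients at risk. This is fair, and is why cause-specific hazard ratios should accompany it. It does not rescue Kaplan-Meier as a probability. Under the SAP's frailty, the 24-month Control probability if nobody died would be 1 - 1/(1+1.2) = 54.5%. The Kaplan-Meier figure of 48.7% is neither that nor the 40.8% who would actually be hospitalized.

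**Conclusion.** The concern holds as a reporting problem. Under the SAP's frailty model, one minus Kaplan-Meier overstates first HF hospitalization by about 6-8 points at 24 months and 13-15 at 5 years; with constant independent hazards the excess reaches about 15 and 30. In these scenarios the excess is larger in Control, so the displayed absolute benefit is too large. CV death is overstated by about 2-3 and 5-11 points.

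Three stronger readings are tempting and not supported.
- The 13-30 point range does not apply to all three endpoints. It fits first HF hospitalization only: just the non-CV deaths compete with CV death, and first CV hospitalization has no planning rate.
- Nothing in the documents makes these curves the basis for labeling or patient information, and no test, alpha or sample size depends on them.
- Censoring of deaths is not written for this item. It is inferred from the choice of estimator and from the rule given for the safety components.

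The 5-year figures carry 12-month planning rates out to 60 months and ignore the MitraClip procedures that Protocol 5.3 allows in Control after the 24-month visit. They indicate order of size; the direction does not depend on them.

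**What to change.** Add to SAP 5.7.4, beside the planned Kaplan-Meier:
- Aalen-Johansen cumulative incidence by arm for CV mortality (non-CV death competing), and for first HF hospitalization and first CV hospitalization (any death competing).
- The same estimator, with death competing, for the long-term primary safety components and for the non-fatal outcomes in the SAP A.2 age subgroups.
- Cause-specific hazard ratios for the arm comparisons.
- A statement that any quoted event probability or absolute difference for these outcomes comes from the cumulative incidence, and an explicit rule for how deaths enter each curve.

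Keep Kaplan-Meier where the protocol specifies it, for comparability, and as the right estimator for all-cause death and for first HF hospitalization or death. Adding instead of replacing leaves the protocol's specification intact and so avoids an amendment.

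The cost is SAP wording and standard software, with no new data. The downside is an extra set of displays whose rates will differ from earlier device reports that used Kaplan-Meier; a short footnote can explain why.

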#### 5.7.5 CPX Sub-Study Endpoint

A sub-study endpoint will be added utilizing peak VO2 as a parameter for cardiopulmonary exercise testing (CPX). CPX testing will be conducted at baseline and 12 months on a total of at least 50 and up to 100 subjects at qualified sites. Mean changes in peak VO2 (ml/kg/min) will be summarized at 12 months from baseline for the subset of patients who complete a CPX test at baseline and 12 months. A comparison of change from baseline between Device and Control groups will be presented. A p-value for the peak VO2 endpoint will be generated for descriptive purposes.

#### 5.7.6 Centers for Medicare and Medicaid Services (CMS) Endpoints

Additional clinical outcomes will be performed for the Centers for Medicare and Medicaid Services (CMS) requirements for the COAPT Trial. The analysis will be performed at the time of the COAPT trial's primary endpoints analyses and these data will be reported separately to the CMS Coverage and Analysis Group at the same time the results are submitted to the Food and Drug Administration (FDA). Refer to Appendix A for the details.

#### 5.8 Power and Sample Size

A total sample size of 610 subjects is planned. The power for the primary safety endpoint when 305 Device group subjects complete 12 months of follow-up is > 95%. The power for the primary effectiveness endpoint with follow-up through 24 months in 610 subjects when the last subject completes 12 months of follow-up is  $\sim$  80%. The overall power for the study for the primary endpoints with the planned randomization of 610 subjects is  $\sim$ 80%.

#### 5.8.1 Primary Safety Endpoint

**Table 1** lists the event rates assumed for the components of the composite primary safety endpoint in the Device group

EventDevice GroupSLDA4%Embolization<0.1%	Endocarditis<0.1%	Mitral Stenosis Confirmed by ECL
That Requires Surgery<0.1%	LVAD Implant, Heart Transplant1%Other Device-related Complications<0.1%	Table 1: Assumptions for Primary Safety Event Rates at 12 Months

Two thousand (2000) simulations were performed to calculate sample size and power for the primary safety endpoint. Assuming 22% mortality and 7.5% attrition at 12 months, a total of 305 subjects in the Device group will provide > 95% power to reject the null hypothesis at the one-sided significance level of 5%.

~6%

#### 5.8.2 Primary Effectiveness Endpoint

That Require Non-elective Cardiovascular Surgery Total

At least ten thousand (10,000) simulations with converged joint frailty model were performed to calculate sample size and power for the primary effectiveness endpoint. With a fixed sample size design, 610 subjects provide approximate 80% power at the one-sided significance level of 5% for the primary effectiveness endpoint.

The following assumptions were made for the calculation of sample size:

- The enrollment rate is based on the actual monthly enrollment numbers from December 2012 to February 2016, then 20 subjects per month, thereafter
- Attrition due to withdrawals at 12 months is 7.5% in both groups
- In the EVEREST High Risk Cohort (N = 211), the lower bound of a 95% confidence interval on the HF hospitalization rate in the period pre-enrollment was ~0.6 per 12 months. The HF hospitalization rate in the Control group is therefore assumed to be 0.6 per 12 months. The HF hospitalization rate in the Device group is assumed to be 0.42 per 12 months (30% Relative Risk Reduction).
- Subjects are followed for a minimum of 12 months. All available follow-up through 24 months at the time of data cut-off will be included in the analysis.
- The mortality rate in the Control group is 27%, and in the Device group is 22%.
- To account for informative censoring of death event, a shared random effect (frailty) model for recurrent events and terminal event is used to simulate recurrent events and

death event data. The correlation between these two processes is introduced by the shared frailty distribution, Gamma distribution with mean of 1 and variance of 1. The frailty is assumed to have the same impact on the hazards for recurrent and terminal event (e.g. frailty exponent is 1). The frailty variance and frailty exponent values are estimated and determined based on the REALISM HR FMR patients data and blinded pooled COAPT roll-in and randomized data as of June, 2016. The key underlying assumptions of the JFM are

- a) The recurrent, terminating, and censoring processes all have continuous distribution so that recurrent events and death cannot happen at the exact same time.
- b) Death event precludes the observation of new recurrent HF hospitalization events, but independent censoring (e.g. withdrawal or lost-to-follow-up) does not interrupt the occurrence of recurrent HF hospitalization events.
- c) The intensity of the current event process at time *t* is a function of subject's process history, covariates, frailty, and being alive just before time *t*. The intensity of the death process at time *t* is a function of covariates, frailty and being alive just before time *t*. Both recurrent process and death process are correlated through the same frailty distribution.
- d) Censoring (administrative censoring) is noninformative, which does not depend on unobserved frailty.

Detailed information about the joint frailty model assumptions, model specification and analysis method and assumed frailty parameters can be found in a separate appendix to the SAP.

• The Joint Frailty Model method was used to estimate the logarithm of 1-RRR for recurrent HF hospitalization event.

